4.6 Group Assignment and Randomization

For Phase 1, participants will be assigned to groups based on when they are enrolled. Once we have a group of 6-10 veterans, we will begin one of the groups (either Tai Chi or Wellness based on instructor availability). We then will gather another 6-10 participants for the next group.

For Phase 2, randomization will occur after baseline assessments for all members of the cohort are completed. A study staff member will make a list of available cohort participants in order of completion of initial telephone screening. The cohort list is password-protected and unavailable to the rest of the staff. Another staff member will then use the list randomizer from Random.org (<https://www.random.org/lists/>) to create a randomly ordered list of the group assignments equally distributed between Tai Chi and Wellness and equal to the size of the cohort, rounding up to an even number. The list of group assignments is then matched with the numbered list of participants. Study staff then call participants to inform them of their condition assignment and the days and times of the group intervention to which they have been assigned.

4.7 Data Analysis

Sample Size Calculation

In this pilot study we are primarily concerned with feasibility and data gathering with a target goal of 48 participants (12 in *Phase One* and 36 in *Phase Two*). Based on our prior experience, we feel confident we can reasonably recruit 48 participants during the study period over 4 waves of recruitment for these intensive (twice per week for 12 weeks) interventions. From our previous experience with remote Tai Chi groups, we found 6 to be an optimal group size as it permitted the instructor to see each participant well on the video screen to provide individualized attention and facilitated a feeling of camaraderie among the participants. For this study's primary outcomes of satisfaction (measured by the CSQ) and credibility of the interventions (measured by the CEQ), we anticipate that more than 70% of the participants will meet the metrics identified. If 26 of 36 participants enrolled in *Phase Two* meet the metric the estimated completion percent would be 72% (95% CI: 55% to 86%). For the primary outcomes of compliance/attendance (measured by sessions and assessments attended), and completion of weekly log sheets, we anticipate that more than 75% of the participants will meet the metrics identified. If 28 of 36 participants enrolled in *Phase Two* meet the metric the estimated completion percent would be 77% (95% CI: 60% to 89%).

Phase Two of this trial will use an individually randomized group treatment trial (IRGT) design, where individual participants are randomized to one of the interventions and the interventions are delivered in small groups. In *Phase Two*, after a cohort of approximately 12 eligible participants are identified, research staff will contact eligible participants by phone to confirm that they still wish to participate in the study and are able to attend sessions at the days and time of the interventions. Once confirmed, half will be randomly assigned to each of the two conditions (Tai Chi and Wellness). If we are unable to recruit 12 Veterans over a one-month recruitment push, we may randomize a smaller cohort of Veterans so that Veterans who have agreed to participate will not be kept waiting too long to begin the interventions.

If we are successful in recruiting more than 12 Veterans over the recruitment push, we may randomize up to 20 Veterans to help ensure that we will end up with an average of 12 Veterans who are able to participate in the groups. Random assignments to condition will be managed by study staff who will generate the randomization scheme. Participants will be randomized in order of completion of initial telephone screening.

Study staff will then call participants to inform them of their condition assignment and the days and times of the group intervention to which they have been assigned.

AIM 1. During Phase One, we will refine and standardize two treatment protocols for Veterans diagnosed with PTSD and chronic musculoskeletal pain. Tai Chi and Wellness interventions will be adapted for delivery via a videoconferencing platform for the population.

Using information gathered from group and individual feedback sessions, we will edit and refine the participant manuals to optimize remote delivery issues such as sound quality, ability to see and follow instructors, instructor ability to view Veterans, and connectivity difficulties. We will also inquire about frequency, duration, and time of day of sessions, class size, ease of use of printed materials and log sheets. We will use adherence and satisfaction data and qualitative feedback to modify the interventions and improve the protocol before moving to *Phase Two*.

AIM 2. During Phase Two, we will determine the feasibility and acceptability of a remotely delivered randomized trial of the two interventions and the assessment protocols.

Feasibility and acceptability will be quantified by evaluating rates of eligibility, enrollment, satisfaction, adherence, retention, and credibility expectancy, and compliance with home practice. Specifically:

- Successful eligibility and enrollment will be indicated by our ability to meet overall recruitment goals (in addition to successfully recruiting a representative sample of women and minorities as projected in the Enrollment Table).
- Treatment satisfaction will be indicated if at least 70% of participants have a score of 3 or greater (corresponding to mostly or very satisfied) on the 1-4 scale of the CSQ.
- Adherence and retention will be determined by meeting the metric of at least 75% of participants attending at least 70% of the treatment sessions and 70% of participants completing all baseline and follow-up assessments.
- Credibility will be measured by the CEQ with at least 70% of participants reporting a credibility rating of 6 or greater on the 9-point scale.
- Compliance with home practice will be measured by 75% of participants completing 70% of weekly log sheets.

Measures to be examined for participant burden for the larger trial will assess PTSD symptom severity, pain levels, global health, and physical functioning at baseline, post-treatment and (for *Phase Two* only) 3-month follow-up. In the qualitative feedback interviews, we will further assess these issues to determine if changes are needed regarding recruitment, retention, adherence, and participant burden. If we do not meet the feasibility goals, we will reevaluate to make refinements before developing protocols for a future large trial.

AIM 3. We will utilize information from this trial to plan and design a large, randomized control study evaluating the efficacy of Tai Chi compared to Wellness for improving outcomes for Veterans with PTSD and chronic musculoskeletal pain.

The Tai Chi and Wellness control protocols developed, revised, and finalized as part of the proposed project will be used in a future larger study designed to evaluate Tai Chi for PTSD and chronic pain. The current study will provide preliminary data on feasibility, acceptability, adherence, and participant burden. In addition, the preliminary trial will allow us to work out technology issues to optimize our use of remote videoconferencing and to develop methods to maximize efficiency for research staff that will help guide the design of this large-scale trial. If we fall short of recruitment and/or retention goals, we will use the information gathered during the qualitative interviews and study staff experience to make further refinements to our remote protocol (e.g. providing additional resources for assistance with technology issues for participants, providing videocams or tablets to all participants, assistance with home setup, etc.).

Qualitative data will be analyzed using an iterative coding process. Individual Interviews will be transcribed and then analyzed by a committee of study staff using a general inductive approach. Raters will independently code several transcripts to identify themes, starting with specific categories such as positive experiences, negative experiences, areas for improvement, and other. Next, the committee will meet to review identified themes, to discuss discrepancies, and to refine the suggested coding rubric. Raters will code the remaining

transcripts and continue to meet until consensus is reached on the identified themes and on the distribution of participant quotes under appropriate themes. The committee will then choose participant quotes that best represent the identified themes. This information will be used to inform refinement of the Tai Chi and Wellness protocols to be used in future studies.

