Posttraumatic stress disorder (PTSD) affects almost one quarter of military Veterans seeking care from Veterans Administration healthcare facilities. PTSD is associated with many health-related issues, especially chronic musculoskeletal pain, and is increasingly considered a systemic disorder, affecting both mind and body. Accessible treatments that address PTSD and chronic pain are urgently needed. Tai Chi is an ancient Chinese exercise that uses an integrated mind-body approach to enhance quality of life. Tai Chi delivered in groups has been shown to improve both mental health and physical health in patients with a variety of chronic conditions. However, no studies to date have examined Tai Chi for PTSD and pain in Veterans. Since the onset of COVID-19, interventions that can be delivered without the need for face-to-face contact are greatly needed. Remote mind-body interventions delivered via videoconferencing platforms can reduce barriers to treatment for Veterans isolated by PTSD-related avoidance, travel related challenges, or public health social distancing restrictions. The proposed study will evaluate the feasibility of remotely delivered Tai Chi for PTSD and pain in Veterans. This trial represents first steps toward a long-term goal of establishing this mind-body treatment to address these maladies for Veterans via a remote videoconferencing platform. In Phase One, the research team will adapt and do a 'dry run' of two existing 12-week, twice per week interventions (Tai Chi and a Wellness control) for delivery via videoconferencing for the study population. In Phase One, the team will recruit 12 participants (6 in each group) and utilize quantitative and qualitative feedback to refine and standardize the interventions. In Phase Two, 36 participants will be randomly assigned over 3 cohorts ($n = 12$ for each cohort, $n = 6$ for each group) to either a Tai Chi or a Wellness group for 12 weeks with a post-treatment and three-month follow up assessment. The feasibility and acceptability of a remotely delivered randomized trial of these two interventions and the assessment protocols will be determined. Feasibility will be quantified using rates of participant eligibility, recruitment, attrition, and adherence to the treatment and assessment protocols. Feasibility will be indicated (1) by the ability to meet recruitment goals, including women and minority participation, and (2) by having at least 75% of participants regularly attend sessions and engage in home practice and 70% complete post-intervention and follow-up assessments. Acceptability will be assessed via participants' ratings on a standardized measure of treatment satisfaction, supplemented by qualitative exit interviews. Acceptability will be indicated by 70% of the participants reporting treatment satisfaction and credibility. Information from this trial will be utilized to design a large, randomized control study evaluating the efficacy of Tai Chi for improving outcomes for Veterans with PTSD and chronic musculoskeletal pain. The proposed study will be pivotal to establish procedures to fully evaluate a novel, accessible, nonpharmacologic approach for symptom management of PTSD and chronic pain in a future large-scale trial of Tai Chi.

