Wellness Control Intervention and Facilitators. We will utilize a Wellness program for the comparison group because this approach has been successfully used in other studies conducted by our team, including a pilot feasibility study conducted with Veterans with PTSD³⁶⁻³⁸. The Wellness intervention will be based on the VA Whole Health Program which helps individuals identify and achieve their personal health goals. The Whole Health Program include modules that address physical activity, personal development, healthy eating and drinking, stress management, relationships, personal surroundings, and spirituality. The Wellness intervention has been adapted with updated information from the VA Whole Health website and other resources to make it suitable for a population with PTSD and chronic pain. Using the SMART goals model, participants will set health and wellness goals each week, and discussions about ways to address potential barriers will be included in this condition. This group will be facilitated by doctoral level psychology staff, and/or psychology trainees and research staff who will be supervised by licensed and credentialed study staff.

For both interventions, study staff will hold "tech sessions" with participants prior to the initial session to ensure that audio and video connections are adequate, and participants know how to navigate the VA-approved videoconferencing platform used (e.g., Cisco Webex or Microsoft Teams). In addition, participants randomized to the Tai Chi group will have the opportunity to provide updates on any physical issues or limitations they would like to make the instructor aware of. Study staff will be available by telephone to help with connectivity

[figure not shown]
and technical issues at the beginning of each session and will call participants who have not logged in to offer assistance.

Participants may be given a water bottle after attending Tai Chi or Wellness class. The water bottles have a logo that says “VA Boston Health & Wellness Research” and display the circular VA emblem. These water bottles may be mailed to participants with a thank you note from the study team.

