After the informed consent document is signed, additional screening procedures covered in the informed consent document will be conducted prior to randomization. The investigators consider this consent process to be an ongoing process maintained throughout the study to provide participants with a continued understanding of the protocol, their participation, and their rights as human research subjects.

All discussions concerning consent will emphasize that participation is voluntary and that the participant's medical care/benefits will be unaffected by his or her decision regarding participation. Participants will be informed that they will be compensated for time and inconvenience at a rate of \$25 for each of the two baseline assessment sessions and \$65 for the post-treatment assessments. Those participants who are recruited for Phase Two will be compensated \$80 for the 3-month follow-up assessment. Participants will also receive \$5 for completing the weekly measures, \$5 for the weekly phone calls with study staff who track home practice/goals, and \$5 for each intervention group session they attend for a grand total of up to \$355 for those in Phase One and \$435 for those in Phase Two. In the event that a participant completes the baseline assessment twice (see paragraph below for scenario where this could occur), the potential total compensation for Phase Two could be \$485. This remuneration for time, inconvenience, and ongoing commitment is not so high as to coerce an individual to participate who would otherwise not participate. Compensation will be provided in one of three ways: 1) gift cards to a national chain store (e.g., Target or Walmart) which would be mailed to them, 2) electronic funds transfers to the participants' bank accounts (bank account information including bank routing number, account number, bank name, account type will need to be confirmed), or by 3) debit card payments using Direct Express (participants will need to request a debit card or provide account information if they already have one) and payments will be made directly to the debit card. If gift cards are sent to participants, a templated thank you letter with a breakdown of the gift card payments will be mailed with the gift cards to ensure participants can keep track of (for their own records) the payments they have received throughout the study and what they were for.

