Credibility/Expectancy Questionnaire (CEQ).	
Assesses participants' perceptions of treatment credibility and outcome expectancy in clinical outcome trials.⁴¹
 
Administered at weeks 1,2,4, and 9 via Qualtrics
 
Metric: At least 70% of participants will report a mean item-score of 6 or greater on the 1-9 scale by week 4 for both credibility and expectancy

Weekly Log Sheets	
Participants will keep logs of homework/practice that will be reported via telephone to the project coordinator weekly during the 12-week intervention period. In the Tai Chi condition, they will record the number of minutes per day spent on home practice. In the Wellness condition, they will record weekly goals.
 
Metric: At least 75% of participants will complete at least 70% of weekly log sheets.

B. Secondary Measures Outcome Measures to Be Administered to Ascertain Burden and Calculate Intra-Class Correlation Coefficients	
Administered at baseline, post-treatment (12-weeks), and 3-month follow-up (24-weeks), for Phase Two only (Note that CAPS-5 will only be administered at baseline and post-treatment for Phase Two)	
Construct and Measure	Description and Citation
PTSD severity: Clinician Administered PTSD Scale – 5th Edition (CAPS-5)	The CAPS-5 is a structured diagnostic interview for PTSD administered by study staff. ⁴² The interviews will take place using a VA approved platform (e.g., Cisco Webex or Microsoft Teams). During Phase Two , this diagnostic interview will be video-recorded, with participant permission and administered at baseline and post-treatment. The recordings will be used to ensure reliability of assessor ratings.
Pain: The Brief Pain Inventory – Short Form (BPI)	The BPI is a self-report measure that examines pain intensity and interference with functioning in various life domains. ^{43,44} Administered via Qualtrics. ^{43, 44}
Medical Outcomes Study Self-Reported Measure of Health Status: 36-Item Short Form Survey (SF-36)	The SF-36 is a 36 item self-report questionnaire that assesses self-perception of health status in the following domains: physical functioning, role limitations due to physical and emotional factors, social functioning, bodily pain, general health, vitality, and mental health. ⁴⁵ Administered via Qualtrics.

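### The home-practice criterion scores only completion of weekly logs, so the Tai Chi minutes collected do not enter it and the pooled figure is a reporting rate

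*Combined protocol and SAP*

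**What the plan says.** The opening summary says feasibility will be shown in part "by having at least 75% of participants regularly attend sessions and engage in home practice". Section 4.7, AIM 2, lists compliance with home practice among the rates that quantify feasibility and acceptability, and gives the rule: "Compliance with home practice will be measured by 75% of participants completing 70% of weekly log sheets".

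Section 4.5, table A (primary measures), has the same metric in the row for weekly log sheets: "At least 75% of participants will complete at least 70% of weekly log sheets". That row introduces the logs as covering homework or practice, "that will be reported via telephone to the project coordinator weekly during the 12-week intervention period". The content then differs by arm. In Tai Chi, "they will record the number of minutes per day spent on home practice". For the comparator: "In the Wellness condition, they will record weekly goals".

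Section 4.3 provides $5 "for the weekly phone calls with study staff who track home practice/goals" and states no link between payment and what is reported. Under the Wellness intervention in 4.1, "participants will set health and wellness goals each week". The sample size text in 4.7 calls the same outcome completion of weekly log sheets, which describes it accurately.

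The plan does not say what makes a log complete, sets no minimum of minutes or days, and specifies no criterion or summary that uses the minutes.

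**The concern.** The goal in the summary and the label in AIM 2 are about practice. The rule beneath them counts reports. A report arrives through a weekly, paid telephone call, so a participant can report reliably while practising little, and the rule cannot tell that person from one who practises every day.

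The pooling adds to this. About half the planned sample records goals and has no practice minutes, so one percentage over both arms cannot be read as a home-practice rate.

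At stake is one primary feasibility criterion. Section 4.7 uses feasibility and adherence results to shape the larger trial, and a missed goal prompts refinement. If the home-practice goal is declared met on reporting alone, that prompt is lost for home practice.

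**Working it through.** **Inputs.** Twelve weekly logs (4.5, table A). Thresholds of 70% of logs and 75% of participants (4.5 and 4.7). Phase Two target of 36, in 3 cohorts with 6 per group (4.1), so 3 × 6 = 18 per arm.

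**1. The plan's own figure.** The sample size text gives 28 of 36 as 77% (95% CI 60% to 89%). The exact (Clopper-Pearson) limits for x of n are the 0.025 quantile of Beta(x, n − x + 1) and the 0.975 quantile of Beta(x + 1, n − x). For 28/36 this gives 77.8% (60.8% to 89.9%). The stated values are these with the decimals cut off. The companion figure of 26/36 comes out at 72.2% (54.8% to 85.8%), matching the stated 72% (55% to 86%). The precision statement therefore stands, but it is precision for log completion.

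**2. What one participant needs.** 0.70 × 12 = 8.4, so 9 logs (9/12 = 75.0%; 8/12 = 66.7% fails). The payments in 4.3 agree with 12 calls. For Phase One, two baseline sessions, the post-treatment assessment and 24 group sessions come to 2 × 25 + 65 + 24 × 5 = $235. The remainder is 355 − 235 = $120, or 24 payments of $5: 12 weekly measures and 12 calls.

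**3. What the study needs.** 0.75 × 36 = 27 participants.

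**4. Case A: a log reporting 0 minutes counts as completed.** Suppose all 18 Tai Chi participants complete 9 logs, each showing 0 minutes, and 9 of 18 Wellness participants complete 9 logs. The result is (18 + 9)/36 = 75.0%. The criterion is met with no recorded Tai Chi practice over 12 × 7 = 84 days. If every log is completed in this way, the result is 36/36. This is a logical bound and not a forecast.

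**5. Case B: a log reporting 0 minutes does not count.** Practice then matters only as zero against more than zero. One minute in each of 9 weeks, 9 minutes in 84 days, scores the same as daily practice.

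**6. Pooling.** Only 18 of 36 participants (50%) record practice minutes. In either case the pooled percentage mixes reports of minutes with reports of goals.

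**7. Precision of a minutes-based figure.** It can apply only to Tai Chi. 0.75 × 18 = 13.5, so 14 participants are needed. 14/18 = 77.8%, exact 95% CI 52.4% to 93.6%, about 41 points wide, against about 29 points for 28/36. Section 4.2 allows up to 10 per group, hence 3 × 10 = 30 in Tai Chi. Then 23/30 = 76.7% (57.7% to 90.1%). The plan gives no minimum size.

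**The case against.** The rule is open and consistent. Sections 4.5 and 4.7 define it in the same way, and AIM 2 states label and measure in one sentence, so a careful reader sees what was counted. Log completion applied identically in both arms is a defensible reporting measure. The summary's goal concerns participants in general and not Tai Chi alone. Minutes are collected and can be described, interviews cover adherence, and no stop/go rule depends on this criterion. All of this stands, and it keeps the consequence small. It does not make the label or the summary's wording match what is scored.

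Two stronger readings are tempting and are not supported. A reader might infer that the plan accepts zero practice as compliance. That depends on a 0-minute log counting as completed, which the documents neither state nor exclude, and nothing in them suggests that such a result is likely. A reader might also infer that Wellness goals have nothing to do with home practice. The log row in 4.5 covers homework or practice and gives each arm its own version, 4.3 pairs practice with goals, and 4.1 has Wellness participants report their goals in the same weekly calls. The documents treat goals as the Wellness counterpart. What remains is narrower: the two contents are not the same quantity, so a single pooled home-practice rate does not describe them.

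**Conclusion.** The point holds as a mismatch between label and measure in a primary feasibility criterion. Followed exactly, the rule is met when at least 27 of 36 participants complete at least 9 of 12 logs. Meeting it shows that participants reported; it does not show that 75% engaged in home practice. With no definition of a completed log, recorded Tai Chi practice could be nil if 0-minute logs count. If they do not count, the amount above zero still has no effect on the result.

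This rests on the planned sizes (36 in total, 18 per arm) and on 12 weekly logs. The documents give no basis for saying how often logs would show little or no practice, so no expected error is claimed. The consequence is modest, but the defect should be corrected before analysis because the data needed are already being collected.

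**What to change.** Change the wording in 4.5 and 4.7, and align the summary:

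1. Rename the current metric 'weekly log completion' and keep it for both arms. State whether a log with 0 minutes, or with no goal, counts as completed.
2. Base the Tai Chi home-practice statement on the recorded minutes: the proportion of participants assigned to Tai Chi who report any practice (more than 0 minutes) in at least 70% of weeks (9 of 12), compared with the 75% goal. Count unreported weeks as not met, and also show them separately so that missing reports are not mistaken for absent practice. This floor establishes engagement and not amount; any higher floor is for the investigators to prespecify.
3. Report Tai Chi minutes and Wellness goal reporting by arm, and do not pool them as one home-practice rate.

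No new data, visits or calls are needed. The costs are a target that is harder to meet, an estimate resting on about 18 participants with the wider interval shown in step 7 of the working, and continued reliance on self-report.
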